11.7. Pharmacokinetic Data

The fazirsiran PK concentration data will be listed as appropriate.

The plasma PK concentration will also be used for population PK analysis, combined with PK data from other clinical studies, using nonlinear mixed effect methods. The Population PK analysis will be supported with separate analysis plans and report.

11.8. Pharmacodynamic Data

Serum AAT Levels: The whole blood collected for PD analysis following multiple doses of fazirsiran or placebo will undergo analysis for PiZ protein and total alpha-1 antitrypsin levels using both a Z-AAT specific assay and a clinical assay. Results, including depth of knockdown as reported by percent change from baseline will be analyzed and summarized by dose cohort and treatment group. For data analysis, batched results using nephelometric assay may be used.

MRI and FibroScan®: Noninvasive imaging using both FibroScan® and MRI (evaluation of liver stiffness with MRE, liver fat with MRI-PDFF (or equivalent MR based measure of liver fat) and liver iron content) will be completed pre-dose and post-dose per the SOA in a standardized fashion. Percent change in quantitative measure of liver stiffness, liver fat and liver iron content from pre-dose to post-dose will be analyzed and summarized by dose cohort and treatment group. MRI images will be collected in a standardized fashion with central image processing and analysis to determine quantitative elastography values. It is acknowledged that not all patients will be able to complete FibroScan® or MRI due to availability or individual medical conditions.

Liver Biopsy Assessments: Liver biopsy will be completed pre-dose and post-dose per the SOA or Early Termination. Secondary and exploratory endpoints will be based on comparison of pre-dose biopsy versus post-dose biopsy. The post-dose biopsy may include a biopsy completed at

Early Termination. Biopsy sample will be taken, prepped, and stored in a standardized manner with biopsy Histologic/IHC reads being completed by an independent blinded central pathologist. Percent change in intrahepatic Z-AAT, changes in PAS/D+ globules (size and number), mRNA, changes in Metavir fibrosis scale, fibrosis gene expression levels, and iron content using biomarkers, special stains, and imaging (Masson's Trichrome, Sirius Red, Iron, if scientifically feasible and sufficient sample available) from pre-dose to post-dose sample will be analyzed and summarized by dose cohort and treatment group. A local reader at each site will be used during Screening to determine eligibility based on presence of fibrosis/cirrhosis per inclusion/exclusion criteria.

11.9. Pre-Specified Subgroup Analyses

Separate pre-specified analysis will be performed for the following subgroups.

- Analysis of efficacy, PD, and safety based on pre-dose Metavir fibrosis Score 0-1 versus 2-3.
- Analysis of efficacy, PD, and safety based on the presence of NAFLD or NASH (defined as presence of hepatic steatosis, inflammation and hepatocyte ballooning on histology) versus no NAFLD and NASH.
- Patients on AAT augmentation will be analyzed separately for changes from baseline in serum AAT levels.

11.10. Analysis Methods

The primary objective of the study is to evaluate the 3 doses of fazirsiran versus placebo and select a single active dose to be evaluated further in later stage studies and used in the open-label phase of this study. In addition to examination of safety, dose selection will be based on the evaluation of the mean percent change from baseline (Day 1, pre-dose) in serum Z-AAT levels through Week 16. The primary efficacy analysis, executed after all enrolled patients reach the Week 16 evaluation, will be performed using a MMRM approach. The repeated measures of the response are the values obtained at the scheduled study Weeks 2, 4, 6, and 16. The model will include fixed categorical effects for treatment, time, week, treatment by week interaction, and a baseline value of serum Z-AAT as a continuous covariate. Restricted maximum likelihood estimation (REML) with an unstructured within-patient covariance structure will be used. If the model fails to converge, alternative covariance structures will be considered.

Based on the stated model, least squares (LS) estimates of the mean percent change from baseline for each treatment group, of the difference for each fazirsiran dose group and pooled placebo, and the corresponding 95% CIs will be reported for each timepoint. P-values from the Week 16 2-sided t-tests of each for each of the 3 dose groups vs placebo group will be evaluated for significance using Hochberg's step-up procedure to adjust for multiplicity of testing. Placebo group will be pooled from placebo patients in 3 dose cohorts. The primary evaluation of interest is at Week 16 timepoint, to be completed in all randomized patients who receive at least one dose

of study treatment (FAS), regardless of the total number of received doses or any intercurrent events (hypothetical estimand).

Secondary endpoints include:

- Subject incidence of treatment-emergent AEs
- Absolute and percent change from baseline in total liver Z-AAT (insoluble + soluble) protein at post-dose biopsy
- Absolute and percent change from baseline in liver Z-AAT soluble protein at postdose biopsy
- Absolute and percent change from baseline in liver Z-AAT insoluble protein at post-dose biopsy
- Absolute and percent change from baseline in liver function tests, including ALT, AST, ALP, GGT, total bilirubin, direct bilirubin and INR at Week 16 and over time through EOS
- Absolute and percent change in serum Z-AAT overtime through EOS
- Change over time in PK measurements of fazirsiran at timepoints specified in the SOA
- Incidence of ADAs
- Change from baseline in Metavir fibrosis stage at post-dose biopsy

If the post-dose liver biopsy is not available, the biopsy completed at Early Termination may be used.

For continuous secondary endpoints, analyses similar to the primary endpoint analysis will be performed. For all continuous longitudinal measures where data is collected at baseline and at more than one pre-scheduled post-baseline visits, a mixed-effects model repeated measures (MMRM) will be applied to evaluate the change from baseline at scheduled visits.

Prior to each analysis of continuous endpoints, the endpoint variable will be evaluated for normality, and as a result, the original data may be transformed to achieve approximate normality. Results of analysis model from transformed data will be appropriately back-transformed to original scale for reporting purpose.

Demographic, PK, PD and safety parameters will be summarized using descriptive statistics (n, mean, SD, % coefficient of variation (CV), geometric mean, geometric %CV, minimum, median, and maximum for continuous parameters; frequency and percentage for categorical parameters).

Sensitivity Analyses of Primary Efficacy Objective

The primary efficacy analysis method, MMRM, is based on the assumption of missing at random (MAR), where patients who discontinue the study prematurely are assumed to have behaved similarly to other patients in the same treatment group had they not dropped out. A sensitivity analysis, performed only if more than 5% of the patients discontinue from the study prematurely, will be performed to evaluate this assumption. The sensitivity analyses will be based on the multiple imputation (MI) control-based imputation method where placebo group is used to impute the missing values of the primary endpoint for the patients in the active treatment group. Specifically, the copy difference in reference method will be used which assumes that patients who withdraw from the active treatment group will have, following the dropout, their efficacy tend toward that of the placebo arm, but starting from the benefit already obtained. Missing endpoint values will be multiply imputed from their approximate posterior predictive distributions, obtained using multivariate imputation by chained equations algorithm. Details of the imputation model will be provided in the SAP. Multiply imputed datasets will be analyzed using the same methods as those in the primary analysis. Results from analysis of each imputed dataset, will be combined using Rubin's combination rule, to produce, if appropriate, a pooled treatment difference and its 95% CI.

A tipping point analysis will also be performed to evaluate the extent of departure from the observed treatment effect in order to arrive at a reversal of study inferences. These analyses will be performed under 2 scenarios regarding the assumptions around missing data mechanism: (1) MAR as applied in the primary analysis using the MMRM model, and (2) Missing Not at Random (MNAR) using the *copy difference* MI as described above.

Exploratory Analyses

The exploratory analyses are designed to investigate the association between treatment with fazirsiran or placebo and various biomarkers. These analyses will be exploratory, and data driven. Additional data, from other clinical trials, are often needed to confirm associations. Some of these exploratory analyses may be reported outside of the clinical study report.

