11.2. Sample Size Considerations

Approximately 36 patients will be enrolled and randomized in the study. The primary efficacy analysis based on serum AAT levels, will be executed after all enrolled patients complete Week 16 visit and will evaluate the difference in mean percent change from baseline at Week 16 between each active dose group and the pooled placebo groups. Patients will be randomized in a 2:1 (active:placebo) ratio within each of the 3 dose cohorts. With 8 patients in each of the 3 active treatment dose groups and 12 patients in the pooled placebo group, the study has 99% global power to declare at least one treatment dose group as different from placebo, assuming the treatment difference from placebo of at least 70 percent points and using a one-sided 2.5% level of significance with Hochberg's step-up adjustment for multiplicity of testing. Furthermore, the study has 97% conjunctive power to detect all dose groups that are truly different from placebo and 99% disjunctive power to detect at least one dose group that is truly different from placebo. The estimate of variability of the primary endpoint is calculated from prior studies to be 35%.

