11.3. Randomization and Stratification

Following Screening, eligible patients will be randomly allocated in a 2:1 ratio within each dose cohort, to receive one of 3 dose levels of fazirsiran (25, 100, or 200 mg) or placebo. Randomization will be performed within each dose cohort to maintain blinding due to different dose volumes in the double-blinded phase.

Metabolic syndrome has been associated with increased risk of developing liver fibrosis in AATD (Clark et al., 2018). Randomization will be stratified by the presence of metabolic syndrome (defined as in Appendix 1) identified at Screening (Alberti et al., 2009). Randomization will also be stratified by presence of NASH (steatosis, inflammation, and ballooning) at Screening based on pre-dose study biopsy. Patients with both NASH and metabolic syndrome will be stratified based on the presence of NASH.

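### Randomisation is stratified by NASH and metabolic syndrome, but the protocol's stated model contains neither factor; if the strata are prognostic, the intervals are conservative and wider than they need be.

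*Protocol*

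**What the plan says.** Protocol section 11.3: "Randomization will be stratified by the presence of metabolic syndrome", and also by NASH as read from the pre-dose study biopsy. A patient with both conditions is placed in the NASH stratum, so there are three levels. The reason given is this: "Metabolic syndrome has been associated with increased risk of developing liver fibrosis in AATD".

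Protocol section 11.10, primary model: "The model will include fixed categorical effects for treatment, time, week, treatment by week interaction, and a baseline value of serum Z-AAT". Baseline enters as a continuous covariate, the covariance is unstructured and estimation is by REML. Neither NASH nor metabolic syndrome appears.

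Section 11.10, secondary endpoints: "For continuous secondary endpoints, analyses similar to the primary endpoint analysis will be performed". No covariates are listed. These endpoints include total, soluble and insoluble liver Z-AAT, ALT, AST and GGT.

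NASH/NAFLD returns only as a subgroup in section 11.9. Metabolic syndrome has no role in the analysis text.

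The supplied SAP is an addendum for the open-label phase. It refers to SAPv3.0 for everything planned earlier, and SAPv3.0 is not among the documents.

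**The concern.** A factor important enough to stratify on is normally carried into the analysis. Stratified allocation makes the groups more alike on that factor, so the true sampling variance of the treatment difference falls. A model without the factor leaves the between-stratum variation in its residual and does not report that reduction. Its standard errors are then too large and its tests conservative, in proportion to how prognostic the factor is.

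The liver endpoints are where this could matter. The protocol itself links metabolic syndrome to liver fibrosis, and section 7.1 guarantees only 24 patients with fibrosis, the group that has a post-dose biopsy. Those patients are spread over three doses and pooled placebo. What is at stake is interval width on the smallest dataset, not a false positive.

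**Working it through.** **1. The plan's own figure.** The inputs are in section 11.2: 8 patients per dose and 12 pooled placebo, "assuming the treatment difference from placebo of at least 70 percent points", an SD of 35, and testing "using a one-sided 2.5% level of significance with Hochberg's step-up adjustment for multiplicity of testing". Section 11.10 uses "P-values from the Week 16 2-sided t-tests"; a two-sided 5% test is the same as a one-sided 2.5% test in the direction of benefit.

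SE = 35 × √(1/8 + 1/12) = 15.98, and 70/15.98 = 4.38. One comparison at one-sided 2.5% therefore has power Φ(4.38 − 1.96) = 99.2%. Simulating Hochberg's procedure over three doses (400,000 trials, pooled variance, 32 df) gives 99.8% for at least one dose and 97.0% for all three. The plan states 99% and 97%, so its figures reproduce.

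**2. What the missing term could cost.** The documents do not say how much outcome variance the strata explain, so that share (R²) is an assumption shown as a range. It is to be read as the share of the variance left after the other model terms. Section 8.6 specifies block randomisation without a block size; blocks of 3 within cohort and stratum were assumed. Stratum mixes of 50/25/25% and 70/15/15% were assumed. Each scenario had 6,000 simulated trials, analysed by a linear model at one time point with and without two stratum indicators.

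Mean 95% CI width, one dose versus pooled placebo, N=36, SD 35, mix 50/25/25:

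| R² | Without stratum | With stratum | Change |
|---|---|---|---|
| 0 | 64.7 | 65.7 | 1.5% wider |
| 0.05 | 64.9 | 64.2 | 1% narrower |
| 0.10 | 65.0 | 62.4 | 4% narrower |
| 0.20 | 64.9 | 58.9 | 9% narrower |
| 0.30 | 65.2 | 55.0 | 16% narrower |

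N=24, both mixes. Only the ratio is usable here, because no SD is given for the liver endpoints:

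| R² | Width with / without stratum |
|---|---|
| 0 | 1.03 to 1.04 |
| 0.05 | 1.01 |
| 0.10 | 0.98 |
| 0.20 | 0.92 to 0.93 |
| 0.30 | 0.86 |

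Linear interpolation puts break-even near R² = 0.03 at N=36 (0.05 × 1.5/2.6). At N=24 it lies near 0.06 to 0.07.

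**3. Direction of the error.** Coverage of the unadjusted 95% CI is about 95 to 96% for R² up to 0.10, 96% at 0.20 and 96 to 97% at 0.30. Adjusted coverage stays near 95%. The mean error of the unadjusted estimate is close to zero.

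Much of the narrowing comes from reporting the standard error correctly; less comes from a better estimate. At N=24 with mix 50/25/25, the true SD of the estimate falls from 18.5 to 18.0 at R² = 0.20 and from 18.1 to 16.9 at R² = 0.30. That is about 3% and 6%, against widths 8% and 14% narrower.

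**4. Remaining imbalance.** Strata are balanced within a cohort, but each dose is compared with placebo pooled over three cohorts. Three cohorts by three strata make nine cells, on average 36/9 = 4 patients each, so incomplete blocks are common. The SD of the difference in NASH share between one dose and pooled placebo is 12 to 13 percentage points at N=36 and 16 to 18 at N=24. Adjustment corrects the estimate for this imbalance but does not prevent it.

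**5. Primary endpoint.** If the residual SD fell to 35 × √0.9 = 33.2 or 35 × √0.8 = 31.3, power for all three doses would move from 97.0% to 98.4% or 99.3%, ignoring the 2 df. There is little left to gain.

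**The case against.** The strongest reply is that the governing document has not been seen. The SAP addendum says that analyses in SAPv3.0 are not repeated, and the protocol defers detail to the SAP. SAPv3.0 may contain the factors. This stands: the finding concerns the protocol's stated model, and the first request is to confirm.

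A reader might infer that the Extended Efficacy and Final analyses are certain to use the unadjusted model. Section 11.11 gives their timing and names no model. The secondary analyses are called similar to the primary one, not identical. Liver Z-AAT has a single planned post-dose biopsy, so the repeated-measures sentence does not cover it.

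The evidence that the strata are prognostic is thin. Section 11.3 ties metabolic syndrome to developing fibrosis, not to change in liver Z-AAT or enzymes. The fibrosis endpoint, Metavir stage, is ordinal and lies outside a fix for continuous endpoints. For serum Z-AAT, section 6.2 says that levels do not depend on fibrosis stage, and nothing is said about NASH or metabolic syndrome. The simulation had no baseline covariate, so any information that the strata share with baseline must not be counted again. This is why R² is defined as what remains after the other terms, and why low values are shown.

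A change of covariates now would also come after selected sponsor representatives saw unblinded Week 16 results. That limits where the adjusted model can be primary. None of this explains why the stated model leaves out the factors that the stated design uses.

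**Conclusion.** The mismatch between sections 11.3 and 11.10 is real, and its consequence is modest and conditional. For an assumed R² of 0.10 to 0.30 beyond the other model terms, adjustment narrows the 95% CI by about 4 to 16% at N=36 and 2 to 14% at N=24. At 0.05 or less there is no useful gain, and at zero the interval widens by about 1.5 to 4%. Stratum mix and block size are also assumptions.

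Two stronger readings are tempting and not supported. One is that the intervals are in fact too wide: that requires prognostic strata, which the documents do not establish for these endpoints. The other is that the omission biases the results or undermines dose selection. It does not: the error is conservative, the estimate is unbiased on average, and the stated 99% and 97% power leaves the primary conclusion out of reach of this point.

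**What to change.** - Confirm whether SAPv3.0 already includes the stratification factors.
- If not, add the three-level stratum as randomised as a fixed effect in the MMRM or ANCOVA for the continuous secondary endpoints not yet unblinded. Pre-specify a rule for collapsing sparse levels, and keep the unadjusted model as a sensitivity analysis.
- For the Week 16 primary result, and for any analysis already unblinded, report the adjusted model as a labelled supportive analysis.
- State how patients without a pre-dose study biopsy were assigned to a NASH stratum. Section 11.3 reads NASH from that biopsy. The synopsis and section 6.1 waive it for patients with a documented no-fibrosis biopsy within a year of Screening, while section 7.1 requires it of everyone. These passages must be reconciled. The stratum recorded at randomisation avoids reclassifying patients, but the documents do not say how it was coded for this group.
- Delete the redundant *time* term from the model sentence, since *week* is the same effect.

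The cost is a short addition to the analysis plan, 2 degrees of freedom and no new data. The downside is intervals at most about 4% wider if the strata carry no information.
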